## 7.5 **Duration of the Study**

For subjects in Cohorts 1-4, the duration of the study clinic visits is approximately 158 days from Screening to the EOS visit. For patients in Cohorts 1b, 3b and 4b, the duration of the study clinic visits is approximately 173 days from Screening to the EOS visit. This does not include the 90-day post-end of study visit follow-up phone call assessing compliance with contraception.

### 8. PATIENT SELECTION

#### 8.1 Number of Patients

Approximately 50 participants may be enrolled in the study (not including replacements or expansion cohort).

#### 8.2 Inclusion Criteria

To be eligible for enrollment, the participating subject must meet all the following inclusion criteria (applicable to all cohorts):

- 1. Able and willing to provide written informed consent prior to the performance of any study specific procedures
- 2. Participants who are willing and able to comply with all study assessments and adhere to the protocol schedule
- 3. A 12-lead ECG at Screening that, in the opinion of the Investigator, has no abnormalities that compromise participant's safety in this study
- 4. Participants using highly effective contraception during the study and for 12 weeks following the last dose of ARO-HSD. Males must not donate sperm for at least 12 weeks post last dose of study treatment. Females of childbearing potential must have a negative urine pregnancy test at Screening and pre-dose on dosing days. Females not of childbearing potential must be post-menopausal (defined as cessation of regular menstrual periods for at least 12 months), confirmed by follicle-stimulating hormone (FSH) consistent with post-menopausal state based on lab reference ranges.
  - Using twice the normal protection of birth control by using a condom AND one other form of either birth control pills (The Pill), depot or injectable birth control, IUD (Intrauterine Device), birth Control Patch (e.g., Ortho Evra), NuvaRing®, OR Surgical sterilization as a single form of birth control: i.e., tubal ligation, hysterectomy, bilateral oophorectomy, vasectomy or equivalently effective surgical form of birth control
  - True subject abstinence for the duration of the study and 12 weeks after the dose of ARO-HSD is acceptable only when in line with the preferred and usual lifestyle of the subject. Periodic abstinence (calendar, symptothermal, postovulation methods), withdrawal (coitus interruptus), spermicides only, and lactational amenorrhoea methods are not considered "true" abstinence and are not acceptable methods of contraception
- 5. No abnormal finding of clinical relevance at the Screening evaluation that in the opinion of the Investigator could adversely impact subject safety during the study or adversely impact study results
- 6. No consistent change in diet or exercise in the month prior to screening or plans to change diet or exercise habits during the study.
- 7. No plans to lose weight during study

Additional Inclusion Criteria for NHV Cohorts 1 through 4

8. Males or females 18 to 55 years of age at Screening

- 9. BMI  $< 35 \text{ kg/m}^2$  at Screening
- 10. Normal ALT and AST at Screening
- 11. No history of or clinical suspicion of diabetes
- 12. No history of or clinical suspicion of liver disease

Additional Inclusion Criteria for patient Cohorts 1b, 3b and 4b

- 13. Males or females 19 to 65 years of age at Screening
- 14. BMI ≤ 40 kg/m² at Screening with no plans to lose weight, increase exercise or otherwise change diet during the study
- 15. Patients agree to have one liver biopsy during the screening period and one at the end of the treatment period for assessment of the treatment effects
- 16. Suspected NASH based on the presence of Screening MRI-PDFF liver fat > 8% AND ALT > ULN [for purposes of this inclusion criterion, ULN is 30 U/L for men and 19 U/L for women (Prati et al., 2002)]. Alternatively, biopsy confirmed NASH within 1 year of screen visit is acceptable for inclusion.
- \* 1 repeat diagnostic test is acceptable within the screening period when determining eligibility.

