BMI (Height and Body Weight)	X	$X^1$							$\mathbf{X}^{1}$		$X^1$		$X^1$	
Concomitant Meds/Therapies	X	X					X	X	X	X	X	X	X	
Electrocardiogram (See Section 10.3.3)	X	X			X	X	X		$(0, 1, 2hr)^2$				X	
Urine Pregnancy Test (WOCP) confirmed negative pre-dose/pre-bx	X	X							pre-dose		pre-bx		X	
FSH (post-menopause)	X													
Urine Drug Screen	X													
Vitals (BP, temp, HR, RR, O 2 )	X	X		X	X	X	X	X	X	X	X	X	X	
HIV, Hep B, C	X													
Labs (heme, coag, chem, lipase, lipids)	X	X					X	X	X	X	X	X	X	
Retinol, RBP, blood for exosomes, cytokine panel		X						X	X	X	X	X	X	
Hemoglobin A1c	X	X											X	
Pro-C3, ELF, Cytokeratin-18		X											X	
Blood PK		X		X	X	X	X	X	pre-dose					
Genotyping (HSD17β13, PNPLA3)	X													
Urinalysis	X	X					X	X	X	X	X	X	X	
Liver Biopsy, FibroScan, MRI-PDFF	X 										X			
Administration of ARO-HSD			X						X					

<sup>1 Body weight only  10-minute window allowed

<sup>3 Liver biopsy can be done at D1, as long it is completed prior to any D1 procedures Version 7.0, 12 March 2021

Arrowhead Pharmaceuticals, Inc. Protocol No.: AROHSD1001

Confidential

Page 11 of 59

Anti-Drug Antibodies		X				X		X	
Adverse Events Collection	х –							X	
Pregnancy phone call									X

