#### Additional Exclusion Criteria for patient Cohorts 1b, 3b and 4b

- 14. Weight loss of more than 5% within 3 months prior to randomization
- 15. Cirrhosis [based on screening biopsy or historical biopsy showing definitive cirrhosis or based on Screening FibroScan > 20 kPa (one retest allowed) or if using an alternate ultrasound elastography method a value indicative of cirrhosis]
- 16. Other well documented causes of chronic liver disease based on medical history (e.g., Wilson's disease, alpha-1 antitrypsin deficiency, hemochromatosis, autoimmune hepatitis)
- 17. Homozygous HSD17βB13 rs72613567 or other loss of function variants at Screening
- 18. Values at Screening representing any of ALT>250 U/L; INR > 1.5, creatinine > 2.0 mg/dL (176.84 umol/L); platelets < 100,000

- 19. Any exclusion to undergoing liver biopsy including concomitant use of anticoagulants, antiplatelet medications, medical history of abnormal bleeding. Patients may be eligible if contraindication anticoagulant/antiplatelet medications have been discontinued for 5 half-lives prior to liver biopsy. NSAIDs must have been discontinued at least 3 days before biopsy and aspirin at least 5 days before biopsy.
- \* 1 repeat diagnostic test is acceptable within the screening period when determining eligibility.

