- *Serology:* Hepatitis B surface antigen, Hepatitis C antibody and HIV antibody screen. If necessary, participants will be counseled by the PI, or medically trained designee, concerning the blood tests for Hepatitis B surface antigen, Hepatitis C and HIV antibodies, and their subsequent results.
- *FSH*: Post-menopausal status will be confirmed by follicle-stimulating hormone (FSH) level consistent with post-menopausal state.
- *Pregnancy:* Females of childbearing potential will have a urine pregnancy test at Screening and pre-dose on dosing days and biopsy days. If urine pregnancy test is positive, dosing or biopsy should not occur, and the patient will be referred to their primary care provider for follow up.
- *Lipid Parameters:* LDL-C, total cholesterol, non-HDL-C, HDL-C, VLDL-C, and triglycerides
- Retinoid pathway markers: retinol, retinol binding protein

- *NASH biomarkers*: ELF [Hyaluronic acid (HA), Procollagen III amino terminal peptide (PIIINP), Tissue inhibitor of metalloproteinase 1 (TIMP-1)], cytokeratin-18, PRO-C3, IL-1β, IL-6, IL-10, INF-gamma, and TNF-α
- *Immunogenicity:* Specified subjects will be assessed for anti-drug antibodies.
- *Genotype:* All patient cohorts will be assessed for HSD17βB13 and PNPLA3 gene variants with the subject's written consent.
- **Exosomal analysis:** blood will be drawn for exosomal analysis of *PNPLA3* and *HSD17B13* if technically feasible.

The Day 1 (pre-dose) value will be used as each participant's baseline value for data analysis purposes or as otherwise specified. If Day 1 or as otherwise specified values are erroneous or not available and repeat blood draw is not possible, the pre-dose value closest to Day 1 (e.g., Screening) may be used as baseline.

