5. DEFINITIONS

Day 1:

For each subject, Day 1 is defined as the first day that protocol-specified study treatment is administered to the subject.

End of Study (EOS) Date:

For each subject, the EOS date is the study completion/early termination date recorded on the eCRF.

Study Day:

For each subject, and for a given date of interest, study day is defined as the number of days relative to Day 1:

- After first dose date: study day = date of interest – Day 1 date + 1
- Prior to first dose date: study day = date of interest – Day 1 date, so that the day prior to Day 1 is Day -1

Study End Date:

The study end date is when the last subject finishes the EOS visit.

Baseline Values:

For all variables, baseline is defined as the last non-missing value obtained prior to the first dose administration on Day 1.

For ECG, if a triplicate is taken prior to the first dose administered on Day 1, baseline is defined as the mean over the set of triplicate assessments.

Analysis Day:

Selected endpoints will be summarized based on Analysis Day defined using Study Day as below.

Scheduled Visit/ Analysis Day	Day 8	Day 15	Day 29	Day 43	Day 57	Day 71	Day 85	Day 99	Day 113
Study Day Window Cohort 1-4	[6,10]	[13,17]	[27,31]	[41, 45]	[55,59]	[69,73]	[83,87]	[97,101]	[111,115]
Study Day Window Cohort 1b,3b,4b	NA	[13,17]	[27,31]	NA	[55,59]	[66,76]	[83,87]	NA	[108,118]

If there is more than one record in a study day window, the analytical record for that specific analysis day will be defined as the record closest to the scheduled visit day. If two records are equidistant from the scheduled visit day, then the earlier record will be chosen. If there are multiple records on the same day, the last record will be used.

Duration of study:

EOS date – Day 1 date + 1

Treatment-Emergent Adverse Event (TEAE):

TEAEs are defined as adverse events occurring on or after the first dose of study treatment through EOS or pre-treatment existing conditions that worsen after the investigational product administration.

Treatment-emergent SAEs (TESAEs):

TESAEs are defined as serious adverse events occurring on or after the first dose of study treatment through EOS or pre-treatment existing conditions that worsen after the investigational product administration.

TEAE at Injection Site:

TEAE occur at the injection site. MedDRA Preferred Terms which are included in LISR are listed in Protocol Section 16.2.

TEAE Related to Local Injection Site Reaction (LISR):

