9.7.2 Analyses of Pharmacodynamic Endpoints

Pharmacodynamic endpoints will be analyzed for cohorts 1b, 3b and 4b and will be created using the Safety Analysis Set.

For NASH biomarkers, descriptive statistics summaries will be provided for following biomarkers:

- ELF which consists of Hyaluronic acid (HA), Procollagen III amino terminal peptide (PIIINP), and Tissue inhibitor of metalloproteinase 1 (TIMP-1)]
- Cytokeratin-18
- PRO-C3
- IL-1 β , IL-6, IL-10
- INF-gamma, and TNF- α
- Liver Fibrosis Score
- Retinol binding protein

- Tumor Necrosis Factor
- Vitamin A

Derived changes and percent changes from baseline to each scheduled postdose visit will be included.

For hepatic imaging (MRI-PDFF and FibroScan), descriptive statistics summaries will be provided. Derived changes and percent changes from baseline to each scheduled postdose visit will be included.

Relative expression for HSD17B13 will be summarized and plotted using a dot plot. Relative expression is defined as $[2^{-(x_n - x_1)} - 1] * 100\%$

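### When a patient qualifies on a repeat MRI-PDFF, the last-value baseline is the scan kept for passing the 8% cut-off, so these patients show an average fall in liver fat without any drug effect

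*Protocol*

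**What the plan says.** Inclusion criterion 16 (Protocol 8.2) reads "Suspected NASH based on the presence of Screening MRI-PDFF liver fat > 8% AND ALT > ULN", with a second route: "Alternatively, biopsy confirmed NASH within 1 year of screen visit is acceptable for inclusion". The footnote below it states that "1 repeat diagnostic test is acceptable within the screening period when determining eligibility". For stiffness, exclusion criterion 15 (Protocol 8.3) refers to "Screening FibroScan > 20 kPa (one retest allowed".

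In Table 2 of the Protocol, the row "Liver Biopsy, FibroScan, MRI-PDFF" is marked at Screening and Day 71 only. Protocol 10.3.6 speaks of MRI readings for eligibility and after dosing. Neither place provides a Day 1 scan.

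SAP section 5: "For all variables, baseline is defined as the last non-missing value obtained prior to the first dose administration on Day 1". Protocol 10.3.5, written for laboratory tests, falls back when Day 1 is unavailable: "the pre-dose value closest to Day 1 (e.g., Screening) may be used as baseline". Applied to imaging, it would select the same scan.

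SAP 9.7.2: "For hepatic imaging (MRI-PDFF and FibroScan), descriptive statistics summaries will be provided", including change and percent change from baseline. Cohorts 1b, 3b and 4b are open label, all active and planned at up to 6 patients each. Change in liver fat is listed among the exploratory endpoints. SAP 2.2 plans no formal hypothesis tests.

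**The concern.** The eligibility scan doubles as the baseline. ALT differs, because it is drawn again before dosing on Day 1. A patient with a first scan at or below 8% and a repeat above 8% enters, and the repeat becomes the baseline. That value is used because it was high enough, so part of its height is on average measurement error, which does not recur at Day 71. The first scan, whose error runs on average the other way, has no role in the baseline.

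The patient cohorts have no placebo group to show or cancel this, and the SAP plans no covariates or subgroups. The artefact points towards benefit. Protocol 12.1 says the results will feed sample size calculations for later studies, and Protocol 5.6 relies on the patient cohorts for Phase 2 planning.

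**Working it through.** **No plan figure to reproduce.** The documents give no scan variability, liver-fat distribution or retest rate. The sizes below are therefore assumptions with ranges.

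**Inputs from the documents.** Cut-off 8%; one repeat; baseline = last pre-dose value; scans at Screening and Day 71; cohort of 6.

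**Assumptions.** True liver fat in the screened population Normal(12,5), Normal(10,4) or Normal(9,3). Within-patient scan SD 0.5, 1.0 or 1.5 points, independent between scans. No drug effect and no true change. Every failed scan is repeated and every patient enters by MRI.

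**Exact check at one point.** Take a true value of 8 and SD 1.
- Passing repeat: E[X2 | X2 > 8] = 8 + 0.399/0.5 = 8.80.
- Failing first scan: E[X1 | X1 ≤ 8] = 8 - 0.399/0.5 = 7.20.
- Last-value baseline: expected change 8 - 8.80 = -0.80.
- Mean of both scans: (7.20 + 8.80)/2 = 8.00, expected change 0.

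**Simulation, 4 million screened patients per setting.** X1, X2 and Day 71 value Y = truth + error. Retest-qualified means X1 ≤ 8 and X2 > 8.

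| Scan SD | Mean change, last-value baseline | Mean percent change | Mean change, baseline = mean of both scans |
|---|---|---|---|
| 0.5 | -0.43 | -5% | +0.01 to +0.02 |
| 1.0 | -0.81 to -0.83 | -9% | +0.05 to +0.08 |
| 1.5 | -1.16 to -1.21 | -12% | +0.10 to +0.16 |

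Ranges are over the three populations. Between 72% and 74% of retest-qualified patients show a fall.

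**Frequency.** Retest-qualified patients make up 2.0% to 13.7% of those enrolled. The chance of at least one in 6 is 1 - (1 - 0.020)^6 ≈ 12% to 1 - (1 - 0.137)^6 ≈ 59%. One such patient moves a 6-patient mean by about -0.4/6 = -0.07 to -1.2/6 = -0.20 points, or about 1 to 2 percentage points of percent change.

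**Cohort level, Normal(12,5), SD 1.**
- Retest-qualified: 0.040 × (-0.81) = -0.03.
- First-pass: 0.960 × (-0.073) = -0.07.
- Total: -0.10.
- With averaging, the retested part becomes 0.040 × 0.08 ≈ 0.00, leaving -0.07.

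Across the nine settings averaging removes about 34% of the expected cohort-level change. In the worst setting, Normal(9,3) with SD 1.5, it goes from about -0.52 to -0.34.

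**Sensitivity to the population model.** With lognormal liver fat (median 8, 12 or 16%, log-SD 0.5) and scan SD 0.5 to 2.0 points (or, for medians 8 and 12%, CV 5% to 15%), retest-qualified patients average -0.32 to -1.90 points (-4% to -19%). Between 70% and 77% show a fall. Averaging gives -0.16 to +0.39. The sign of the last-value bias is the same in every setting.

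**The case against.** The other side has five arguments.

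- **Small against noise.** Scan error alone gives a 6-patient mean change an SD of SD × √(2/6), which is 0.29 to 0.87 points. Retest-qualified patients contribute only about -0.01 to -0.17 to the expected cohort mean. This stands.
- **Frequency is an upper bound.** The footnote permits a repeat but does not require one, and the biopsy route has no liver-fat cut-off. This stands.
- **The footnote does not name MRI.** It follows directly on the MRI criterion, and laboratory repeats have their own rule in Protocol 10.3.5. Reading it to include the scan is natural, though not explicit.
- **The last-value rule is prespecified and uniform, and the endpoint is exploratory.** True, and it limits the consequence to a descriptive estimate. Uniformity does not remove a bias whose direction is known.
- **Averaging leaves most of the artefact.** True: about two thirds comes from first-pass patients, whose single scan was also required to exceed 8%.

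A reader might infer that every retested patient will show a false fall, or that the failed scan is lost. The documents support neither. The bias is an average, and roughly a quarter of these patients would show no fall. SAP section 5 only chooses the analysis baseline; nothing says the first scan is removed from the data.

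**Conclusion.** The point holds for patients who qualify on a repeat MRI-PDFF. Their baseline is a value selected for passing, and with no drug effect their average change is about -0.4 to -1.2 points (-5% to -12%) for an assumed scan SD of 0.5 to 1.5 points. The direction follows from the text for any non-zero scan error; the size rests on the assumptions above. The 12% to 59% chance of at least one such patient in 6 is an upper bound.

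It would go too far to conclude that the liver-fat result as a whole is invalid, or that a type I error is at stake: no hypothesis is tested, and the cohort-level shift is modest. It would also be wrong to think that a rule for retests cures the problem, since about two thirds of the expected cohort-level shift remains.

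For FibroScan the mechanism is the mirror image. A retest at or below 20 kPa becomes the baseline, and the average change is biased upward. Its size cannot be estimated from the documents, and FibroScan change is a planned summary rather than a listed exploratory endpoint.

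The change is worth making because the correction for retested patients uses data already collected.

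**What to change.** 1. In SAP section 5, add that when MRI-PDFF is repeated during screening, or FibroScan is repeated by the same method, baseline is the mean of all valid pre-dose measurements. The restriction to one method matters because Protocol 10.3.6 allows an equivalent elastography technique.
2. In the imaging listing, flag patients who qualified on a repeat and show both pre-dose values.
3. In the study report, state that patients entering by MRI-PDFF were selected on the scan used as baseline, and that the remaining regression to the mean is uncontrolled in these single-arm cohorts.
4. Record the exception in SAP section 10, which currently reports no departures from the protocol analyses.

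The cost is one SAP sentence, one derivation and one flag, with no new data and no change to eligibility. The price is a departure from the single baseline rule for two variables, with baselines of unequal precision between patients. Only a pre-dose scan not used for eligibility would bring the expected null change to zero in both groups; the current schedule has none.

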#### 8.3 Exclusion Criteria

A potential subject will be excluded from the study if *any* of the following criteria apply (applicable to all cohorts):

- 1. Pregnant or lactating females
- 2. Human immunodeficiency virus infection, as shown by the presence of anti-HIV antibody (sero-positive)
- 3. Seropositive for HBV (HBsAg positive at Screening) or HCV (detectable HCV RNA at Screening). Cured HCV (positive antibody test without detectable HCV RNA is acceptable if HCV RNA has been negative for at least 2 years).
- 4. Uncontrolled hypertension (Systolic BP > 170 and diastolic BP > 100 mmHg at Screening). Patients may rescreen once BP is successfully controlled.
- 5. A history of torsades de pointes, ventricular rhythm disturbances (e.g., ventricular tachycardia or fibrillation), heart block (excluding first-degree block, being PR interval prolongation only), congenital long QT syndrome or new ST segment elevation or depression or new Q-wave on ECG. Participants with a history of atrial arrhythmias should be discussed with the Medical Monitor

- 6. Symptomatic heart failure (per NYHA guidelines), unstable angina, myocardial infarction, severe cardiovascular disease (ejection fraction < 20%. Transient ischemic attack (TIA) or cerebrovascular accident (CVA) within 6 months prior to Screening
- 7. History of malignancy except for adequately treated basal cell carcinoma, squamous cell skin cancer, superficial bladder tumors, or in situ cervical cancer. Participants with other curatively treated malignancies who have no evidence of metastatic disease and > 1-year disease-free interval may be entered following approval by the Medical Monitor
- 8. History of major surgery within 1 month prior to Screening
- 9. Excessive use of alcohol within three months prior to the Screening visit (i.e., > 14 units per week or > 4 units on a given day for men and > 7 units per week or > 3 units on a given day for women [1 unit = 150 mL of wine, 360 mL of beer, or 45 mL of 40% alcohol])
- 10. Use of illicit drugs (such as cocaine or phencyclidine [PCP]) within 1 year prior to the Screening visit or positive urine drug screen at Screening (a urine drug screen positive for benzodiazepines, amphetamines, opioids or cannabis is acceptable for enrollment if the positive test is due to a substance used for medical reasons)
- 11. Use of an investigational agent or device within 30 days prior to dosing or current participation in an investigational study involving a therapeutic intervention
- 12. Blood donation (≥ 500 mL) within 7 days prior to study treatment administration
- 13. Any concomitant medical or psychiatric condition or social situation that would make it difficult to comply with protocol requirements or put the participant at additional safety risk

#### Additional Exclusion Criteria for patient Cohorts 1b, 3b and 4b

- 14. Weight loss of more than 5% within 3 months prior to randomization
- 15. Cirrhosis [based on screening biopsy or historical biopsy showing definitive cirrhosis or based on Screening FibroScan > 20 kPa (one retest allowed) or if using an alternate ultrasound elastography method a value indicative of cirrhosis]
- 16. Other well documented causes of chronic liver disease based on medical history (e.g., Wilson's disease, alpha-1 antitrypsin deficiency, hemochromatosis, autoimmune hepatitis)
- 17. Homozygous HSD17βB13 rs72613567 or other loss of function variants at Screening
- 18. Values at Screening representing any of ALT>250 U/L; INR > 1.5, creatinine > 2.0 mg/dL (176.84 umol/L); platelets < 100,000

- 19. Any exclusion to undergoing liver biopsy including concomitant use of anticoagulants, antiplatelet medications, medical history of abnormal bleeding. Patients may be eligible if contraindication anticoagulant/antiplatelet medications have been discontinued for 5 half-lives prior to liver biopsy. NSAIDs must have been discontinued at least 3 days before biopsy and aspirin at least 5 days before biopsy.
- \* 1 repeat diagnostic test is acceptable within the screening period when determining eligibility.

